### 2.2.1. Additional information for endpoints of COPD progression

#### Exacerbation (Chapter 7)

Times of exacerbation 0-18m (baseline to Month 18, same for the followings) and 0-30m will be summarised. Rate of exacerbation (yearly) will be estimated based on negative binomial distribution at the end of study.

CID and its components are defined in [7.2](#). Percentage of participants who have any event(s) in 0-6m, 6-18m, 18-30m will be presented.

## **Clinical feature Analyses (Chapter 8)**

Spirometry at each planned visit (baseline, Month 6, Month 18 and Month 30) and the post-baseline change from baseline will be summarised. FEV1 and FVC will be analysed using MMRM model. Analysis window for post-baseline visits of spirometry is defined as planned visit date  $\pm 90$  days. Spirometry results out-of-window will be regarded as missing.

Rate of change (decline) in FEV1 and FVC (yearly, unit ml/year) will be analysed at the end of study. All results regardless of the visit window will be included in the analyses.

COPD GOLD grade change, as the result of change of spirometry. Spirometry results out-of-window (visit window is  $\pm 90$  days) will be regarded as missing.

## **Patient Report Outcome (PRO) and Activity (Chapter 9)**

The PROs and activities are not only collected by on site visit, and please refer to Protocol schedule of activities for further details.

CAT at each planned visits, including phone call visits, will be summarised.

EXACT and E-RS are collected for 2 period of 180 days after baseline and Month 18. Summary of these 2 questionnaires will be based on the mean score during baseline (defined as study D1-D7), Month 1-6 (defined as up to 180 days from study D8) and Month 18-24 (defined as up to 180 days from Month 18 visit).

Daily steps collected by wrist band is used to stands for physical activity measures. Daily steps are collected for 2 period of approximately 30 days after baseline and Month 18. Summary of daily steps will be based on the participants mean steps during baseline (defined as study D1-D7), Month 1 (defined as up to 30 days from study D8) and Month 18 (defined as up to 30 days from Month 18 visit).

HRCT data will be summarised at baseline and the end of study. In addition, for participants who had exacerbation visits (a pre-defined special unscheduled visit happened after exacerbation observed), the HRCT data of these visits will be summarised and compared with baseline and the end of study.

[figure not shown]

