## 2. SCHEDULE OF ACTIVITIES (SOA)

Study participants will be followed up for 2.5 years and a total of 4 clinic visits (baseline, 6, 18, and 30 months) are scheduled for study assessments with a visit window of  $\pm 30$  days (Table 1). Baseline data will be collected at Visit 1. In addition, COPD and chronic bronchitis participants will be contacted by phone on trimonthly basis within  $\pm 7$  days of the planned date to assess the CAT and to collect information on exacerbation rates and COPD medications; healthy controls will be contacted by phone on trimonthly basis within  $\pm 7$  days of the planned date to assess the CAT only. For the 4 clinic visits (V1-V4), all the participants should be clinically stable with no exacerbation or other acute medical event for at least 30 days prior to each scheduled visit.

A subset of participants will receive additional digital and biomarker assessments during the study. If moderate/severe exacerbations are reported by the participants or detected by the investigators during the acute phase of event, the participant will be invited to site hospital for an exacerbation visit. If multiple moderate/severe exacerbations are reported or detected, the participants will be contacted in consecutive manner for an exacerbation visit. The total number of the exacerbation visits should be no more than 2, with an interval of at least 21 days. Please note, for the sub-cohort, the planned clinic visits should be scheduled with an interval of at least 60 days after a completed exacerbation visit. When any participant in the sub-cohort is implemented an exacerbation visit, then his/her next planned clinic visit (V2-V4) should be scheduled at least 60 days after completing this exacerbation visit. In this case, the participant's clinic visit may be scheduled outside of the time window of  $\pm 30$  days, which will not be considered as a Protocol Deviation (for more information please refer to the Protocol Deviation Management Plan [PDMP] for this study).

**Table 1** Time and event table

| Protocol Activity                          | Screen/Baseline |               |               |               | Study visit |   |
|--|-----------------|---------------|---------------|---------------|-------------|---|
|  | V1              | V2            | V3            | V4            | EW          | Exacerbation visit ( $\le 2$ )  |

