| Protocol Activity   | Screen/Baseline | Study visit     |   |                 |   |   |
|---|-----------------|-----------------|---|-----------------|---|---|
|   |                 | X  | - | X  | - |   |
| Monthly CAT   | X  | -               | - | X  | - | - |
| Blood biomarkers (inclusive of serum sRAGE, CC16, IP-10, HbA1c) | X               | -               | - | X               | X | X |
| Sputum cytology                                    | X               | -               | - | X               | X | X |
| Sputum microbiome                                  | X               | -               | - | X               | X | X |

CAT=COPD assessment test, COPD=Chronic Obstructive Pulmonary Disease, HRCT=High-resolution computed tomography, EW=Early Withdrawal, EXACT=EXAceration of COPD Tool; SGRQ-C=St.George's Respiratory Questionnaire for COPD. CAPTURE=COPD Assessment in Primary Care to Identify Undiagnosed Respiratory Disease and Exacerbation Risk

1. Exacerbation visits only apply to subjects included in the Biomarker & Digital sub-cohort. Moderate exacerbations are defined as COPD exacerbations that require either systemic corticosteroids (intramuscular (IM), intravenous, or oral) and/or antibiotics. Severe exacerbations are defined as COPD exacerbations requiring hospitalization or result in death.
2. Informed consent must be conducted at the screen visit prior to performing any study procedures.
3. For COPD participants only;
4. When a trimonthly telephone interview overlaps a clinical visit, the COPD exacerbation assessment, COPD medication and treatment questionnaires will be completed at the clinic visit. A month is defined as 30 days in this study.
5. Data collection of COPD exacerbation assessment, COPD medication and treatment are not required for the healthy control participants.
6. CT scan should only be performed at withdrawal visit if the last study CT performed was more than a year ago. Inspiratory and expiratory HRCT scans are required at Visit 1 and Visit 4, while only inspiratory scan will be conducted on exacerbation visit. The CT scan for an exacerbation visit should only be performed if the last study CT scan performed was more than 14 days.
7. Pre-and post- bronchodilator values of spirometry test will be collected at each site visit.

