#### 10.1.2. Study Design Considerations

This is a longitudinal study in subjects with COPD and controls. The follow-up period is 2.5 years with scheduled clinic visits at study entry, 6 months, 18 months, and 30 months.

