#### Endpoint: FEV1 and FVC

Additional analysis of FEV1 and FVC will be provided in Full Population, described as followed.

Pre- and post-bronchodilator FEV1 at each visit, and their change from baseline will be summarized descriptively. N(missing), mean, sd, median, Q1, Q3, Minimum and Maximum will be provided. A same descriptive summary will be provided for FVC.

A line plot of pre- and post-bronchodilator FEV1 and FVC will be provided, showing the mean value of pre- and post-bronchodilator FEV1 and FVC at each visit on the same plot.

Analysis of Pre- and Post-bronchodilator FEV1 at each visit using mixed models with repeated measures (MMRM) will be provided. A same analysis will be provided for FVC. Details of MMRM is described in the following table.

Endpoint / Variables
Change of FEV 1 from baseline in milliliters (mL)

Change of FVC from baseline in milliliters (mL)
Model Specification

 
• The Mixed Models Repeated Measures (MMRM) analysis FEV1 or FVC at every on-site visit (6 months, 18 months and 30 months).
 
• Terms in the model: 
 
• Response: FEV1 or FVC change from baseline at each visit.
 
• Population: Full population
 
• Categorical: visit, type of subjects (i.e. GOLD I-IV, chronic bronchitis, healthy control), gender, smoking status, site (type of hospital), maintenance treatment (Y/N) and ICS containing (Y/N), Childhood chest disease (Y/N) and biomass fuel exposure (Y/N).
 
• Continuous: age, baseline FEV1, count of COPD exacerbations
 
• Interaction: type of subjects*visit, baseline*visit
 
• Repeated: visit
 
 
 
• The model will be fitted with an unstructured variance-covariance matrix. If the model fails to converge, then alternative covariance structures may be investigated.
 
• The Kenward and Roger method (KR) for approximating the denominator degrees of freedom and correcting for bias in the estimated variance-covariance of the fixed effects will be used.
 
• Comparison with Health Control will be provided.
 
• Models will be fitted for pre- and post-bronchodilator FEV1 and FVC, respectively.
 

Model Results Presentation

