### **9.3. EXACT and E-RS**

The EXACT and E-RS are questionnaire-based symptom scores. E-RS utilizes 11 respiratory symptom items from the existing and validated 14-item EXACT. The EXACT/E-RS are collected by daily digital diary, the measurements last for 180 days (6 months) from Visit 1 (baseline) and Visit 3 (month 18). Baseline of EXACT/E-RS is defined as the average of D1-D7. The follow up period start from D8, e.g. 1-6 month is defined as up to 180 days from D8, etc.

Frequency of EXACT events will be summarised by 0, 1, more than 2 for 1-6 month and 18-24 month in participants with at least 3 consecutive records, or 7 records. EXACT event is defined as an increase in EXACT score  $\geq 9$  points for 3 days or  $\geq 12$  points for 2 days, above baseline (average in 7-day period). For more details, please refer to [Patient-reported Outcome](#).

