### **Endpoint: Number of Visits**

A descriptive summary of patient visits (Total, outpatient visits, emergency visits, and hospitalization) during the entire study period will be provided, both COPD related and non-COPD related visits will be presented.

A summary by season for COPD-related visits will also be provided, the definition of season is:

- Spring (Mar, Apr, May)
- Summer (Jun, Jul, Aug)
- Autumn (Sep, Oct, Nov)
- Winter (Dec, Jan, Feb)

The total follow-up period (year) and a summary of crude rate of COPD related and non-COPD related visits and the subcategory visits will be provided in a same table. The total follow-up and crude rate are defined as:

$$Total\ Followup\ Time = \sum (Last\ Visit\ Date - First\ Visit\ Date + 1)$$

$$Crude\ Rate = \frac{Sum\ of\ Number\ of\ Visits}{Total\ Followup\ Time\ (year)}$$

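### SAP 14.2 reports visits and cost by season without seasonal person-time, and steps, diary and clinic spirometry are re-measured about half a year out of phase with baseline, so these summaries can mix season with follow-up or change

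*SAP*

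**What the plan says.** - **Clinic schedule.** Protocol section 2 states that "a total of 4 clinic visits (baseline, 6, 18, and 30 months) are scheduled for study assessments", and a footnote to its Table 1 adds "A month is defined as 30 days in this study". Visits 2, 3 and 4 are therefore planned for days 180, 540 and 900.
- **Steps and diary (sub-cohort).** For the wrist band, SAP 2.2.1 states: "Daily steps are collected for 2 period of approximately 30 days after baseline and Month 18". For the diary, "EXACT and E-RS are collected for 2 period of 180 days after baseline and Month 18". SAP 9.3 and 9.4 summarise both by period.
- **Spirometry.** In the SAP 8.1 MMRM the response is FEV1 "or FVC change from baseline at each visit". Neither that model nor the slope model lists a season or calendar term. Each arm is compared with healthy controls.
- **Healthcare use.** In SAP 14.2, "A summary by season for COPD-related visits will also be provided, the definition of season is" followed by four three-month blocks. Total cost is also summarised by season. The one rate defined, the crude rate, divides by total follow-up time; no person-time is defined within a season.

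**The concern.** A raw count by season is a rate by season only if each season was observed for the same length of time. A follow-up of two and a half years cannot give that for an individual. It gives it for a group only when enrolment is spread over the year. Without a denominator, a reader of the seasonal table cannot tell a bad winter from a long one.

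The same half-year gap affects change over time. If baseline is in winter, the second step period falls in summer and the two diary periods cover complementary halves of the year. A difference between periods then contains disease change plus whatever season does to walking and symptoms. Changes in physical activity and in E-RS are named progression endpoints, and SAP 9.3 and 9.4 plan no control contrast for them.

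**Working it through.** **The plan's own figure.** The documents give no figure on season. The only design figure that uses the visit schedule is the FEV1 slope precision (protocol 10.1.3, P = 4, D = 2.5):

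- σ_p = √[3.8² + 12·3·233²/(2.5²·4·5)] = 125.1, as stated.
- Half-width with 525 per group = 1.96 × 125.1 × √(2/525) = 15.1 mL/year, against 15 stated.

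It reproduces, and serves below only as a yardstick.

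**Phase.** Days 180, 540 and 900, modulo 365, fall 180, 175 and 170 days past the baseline calendar date. The first diary period (180 days from study day 8) covers day offsets 7–186. The second covers 540–719, which modulo 365 is 175–354. They share offsets 175–186, which is 12 days.

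**Season exposure, one participant.** 900 = 2 × 365 + 170. From 1 March, two full years give 184 spring, 184 summer, 182 autumn and 180 winter days. The remaining 170 days add 92 spring and 78 summer. Totals are 276, 262, 182 and 180, and 276/180 = 1.53.

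**Season exposure, pooled** (assumed enrolment patterns, even by day within each period, 900 days each):

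| Enrolment | Most vs least covered season, mean days | Ratio |
|---|---|---|
| All March–May | 275 summer vs 180 winter | 1.53 |
| All March–August | 253 summer vs 197 winter | 1.28 |
| 75% March–August | 240 vs 210 | 1.14 |
| 60% March–August | 232 vs 217 | 1.07 |
| Even over the year | 227 vs 222 | 1.02 |

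Counting 913 days from the first of each month instead gives 1.34, 1.17, 1.08 and 1.02 for the last four rows. With equal risk in all seasons, raw counts differ by these ratios. The distortion can also hide an effect. With March–May enrolment and a winter rate 1.5 times the summer rate (assumed), expected counts are in the ratio 180 × 1.5 = 270 to 275, so the table would look flat.

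**Change from baseline.** Let S be the peak-to-trough seasonal swing (assumed, sinusoidal).

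- Everyone enrolled at the peak: a clinic change is shifted by about S, steps by 0.98–0.99 S, and a diary mean by at most 0.64 S.
- Enrolment even within one half-year: clinic shift 2S/π = 0.64 S.
- A 60/40 split between half-years: 0.2 × 0.64 S = 0.13 S.
- Even over the year: 0.

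For FEV1 with S = 20, 50 or 100 mL, one-half-year enrolment gives 12.7, 31.9 or 63.7 mL. A 60/40 split gives 2.5, 6.4 or 12.7 mL.

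**EXACT events.** Assume no true change and a sinusoidal rate, peaking in mid-January at 1.5 or 2 times its summer low. The ratio of expected events, second diary period to first, is:

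- September–November enrolment: about 0.79 or 0.68.
- September–February: about 0.89 or 0.82.
- March–August: about 1.13 or 1.22.
- Even: 1.00.

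**FEV1 slope.** On times 0, 0.5, 1.5 and 2.5 years (mean 1.125, Sxx = 3.6875), a baseline at the peak and later visits at the trough give a least-squares bias of −1.125 S/3.6875 = −0.305 S per year. For S = 10, 20, 50 and 100 mL that is 3.1, 6.1, 15.3 and 30.5 mL/year, against a planned half-width of 15. On the post-baseline visits alone it is about 0, because those visits share a season.

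**The case against.** The strongest reply is that group-level bias needs uneven enrolment, and nothing in the documents shows it. Protocol 5.2 encourages consecutive recruitment. Amendment 2 (June 2021) was still adding a site to help enrolment of about 2,000 people, which hardly suggests a three-month window. With even enrolment the mean shift is zero and season exposure is nearly equal. This stands. A reader might infer from the schedule that change over time in this study is confounded with season; the documents support that only within participants.

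Three further protections also stand:

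- **CAT.** It is also taken by phone every three months (protocol 9.2.6.1) and summarised at those calls. Months 12 and 24 fall in the baseline season, so CAT change can be separated from season.
- **Rate of FEV1 decline.** Protocol 10.2.3.1 uses only post-baseline values as the response, which leaves almost no seasonal bias. SAP 8.1 says each visit and does not state whether Visit 1 is a response, so the exposure shown above is conditional on that reading.
- **Healthy-control contrasts.** A seasonal effect common to the arms cancels when they enrol over the same months, even if those months are uneven through the year.

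The ±90-day analysis window (SAP 2.1) also allows offsets from 80 to 270 days, so not every visit lies exactly opposite baseline. The event ratios above are not planned SAP outputs; SAP 9.3 tabulates event frequency by period and leaves the comparison to the reader. Finally, a season covariate is weak where it is needed most. Season hardly varies across one participant's follow-up visits, so with clustered enrolment it can barely be told apart from change since baseline.

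None of this supplies the missing denominator in SAP 14.2. Early withdrawal also alters seasonal person-time. Even enrolment overall would not guarantee it within each arm, the sub-cohort, or the HRU population, which excludes five sites.

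**Conclusion.** The point holds in two parts.

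The firmer part is SAP 14.2: seasonal counts and costs have no seasonal time at risk. The resulting distortion is up to about 1.5-fold for one participant. Pooled, it runs from 1.02 (even enrolment) to about 1.5 (all enrolled in one three-month season).

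The second part is conditional. Pooled change in steps, E-RS/EXACT and clinic FEV1/FVC is mixed with season within each participant, and in group means only to the extent that Visit 1 dates were uneven over the year. Its size depends on a seasonal swing and an enrolment pattern that the documents do not give; the figures above are ranges under assumptions, not estimates of bias in this study.

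The study is descriptive with no formal inference (SAP 2.4). That limits the consequence but does not make a count without a denominator interpretable. The plan should be changed, though the schedule itself need not be.

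**What to change.** 1. **SAP 14.2.** Report COPD-related visits and costs per person-year at risk within each season, by the four-season definition already there. State which dates bound the time at risk. The section says scheduled-visit information is not in the hospital database, so Visit 1 and end-of-follow-up dates would have to come from the study database.
2. **SAP 6, 9.3 and 9.4.** Tabulate month of Visit 1 by arm, for the Full and Sub-cohort populations. Show the steps and E-RS/EXACT period summaries by season of Visit 1 as well as pooled. If the table shows even enrolment, one sentence in the report settles the matter.
3. **SAP 8.1, sensitivity analysis only.** Add season of assessment to the FEV1/FVC change-from-baseline MMRM. State whether Visit 1 is a response in the slope model, and add season there only if it is. Say in advance that season and change since baseline are poorly separable if enrolment was clustered.

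The cost is SAP wording, modest programming and smaller cells in the stratified displays. Visit dates are already collected, and no visit or procedure changes.

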### **2.2.2. Additional information for other endpoints**

Treatment pattern will be analysed in baseline (up to 90 days prior baseline to baseline), 0-6m, 6-18m and 18-30m.

HRU data will be analysed in total and by season, as defined in [14.2](#) .

Unless otherwise specified, the other endpoints will be analysed by visits.

## 2.3. Study Design

## 2.4. Statistical Hypotheses / Statistical Analyses

This study is mainly descriptive with no formal inference associated with the study objectives. Nominal P-value may be provided as reference. 2-sided 95% confidence intervals will accompany all effect estimates.

### 3. PLANNED ANALYSES

#### 3.1. Interim Analyses

Interim analyses will be performed in the following sequential steps:

1. All participants have completed each clinical visit as defined in the protocol.
2. All required database cleaning activities in accordance with the Data Management Plan (DMP) have been completed and interim database release (DBR) and database freeze (DBF) has been declared by Data Management.

At the end of Visit 1, data from subjects in the full population will be used to address questions associated with subject phenotypes, characterisation of disease severity, and inter-individual variability of each endpoint. At the end of visit 2, 3 and 4, available clinical, radiological, biomarker, Patient-reported Outcomes (PRO), and health economics endpoints will be assessed based on the appropriate population.

**Table 1. Overview of planned interim analyses**

Time points	Analyses	Population	Data availability
Last Subject Complete Visit 1 (baseline)	Interim analyses 1	Full/sub-cohort	Study population analyses (baseline) Phenotypic analyses (baseline)
Last Subject Complete Visit 2 (month 6)	Interim analyses 2	Full/sub-cohort	Disease progression analyses Study population analysis (for Radiological examination) Treatment pattern and Health resource utilization/cost analyses
Last Subject Complete Visit 3 (month 18)	Interim analyses 3	Full/sub-cohort	Disease progression analyses (Exacerbation analysis)
Last Subject Complete Visit 4 (month 30)	Final analyses	Full/sub-cohort	Study population analyses Disease progression analyses Phenotypic analyses HRCT analyses Treatment pattern and Health resource utilization/cost Safety analyses

#### 3.2. Final Analyses

The final planned primary analyses will be performed after the completion of the following sequential steps:

1. All subjects have completed/withdraw the study as defined in the protocol.
2. All required database cleaning activities have been completed and final database release and database freeze has been declared by Data Management.

## 4. ANALYSIS POPULATIONS

**Table 2. Summary of Study Populations**

Population	Definition / Criteria	Analyses Evaluated
All Screened	
The All Screened Population will consist of all participants who sign the ICF to participate in the clinical trial.
 
Participants in this population will be used for screen failure summary.
	
 
• Study Population
 

Full	The Full Population will consist of all subjects (except subject PPD ) who are enrolled in the study and attend Visit 1, and not withdraw informed consent.	
 
• Study Population
 
• Disease Progression Analyses
 
• Phenotypic Analyses
 
• Treatment Pattern and Healthcare Resource Utilization/Cost
 
• Safety Analyses
 

Sub-cohort	Sub-cohort is a subset of Full population. Subjects who are enrolled in the Biomarker & Digital sub-cohort and who provided at least one additional sub-cohort assessment.	
 
• Study Population
 
• Disease Progression Analyses
 
• Phenotypic Analyses
 
• Treatment Pattern and Healthcare Resource Utilization/Cost
 
• HRCT analysis
 

HRU	HRU is a subset of Full population. The following sites are not feasible to capture data by HIS, thus the patients enrolled from the following sites will be excluded from HRU analysis: 238160, 238222, 237965, 237971, 238155.	
 
• Treatment Pattern and Healthcare Resource Utilization/Cost
 

[figure not shown]
\*: Subject PPD cannot be categorized into either of the study arms (COPD patients, Chronic Bronchitis patients or Healthy Control), thus excluded from the Full population.

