### **8.2. Withdrawal from the Study**

- A participant may withdraw from the study at any time at his/her own request, or may be withdrawn at any time at the discretion of the investigator for safety, behavioural, compliance or administrative reasons.
- A subject will be considered withdrawn from the study if he/she joins any clinical studies where investigational drugs are tested.
- If the participant withdraws consent for disclosure of future information, the sponsor may retain and continue to use any data collected before such a withdrawal of consent. If a participant withdraws consent for disclosure, the site may use any publicly information to determine vital status at the end of the study and this information would be included in the final analyses.
- If a participant withdraws from the study, he/she may request destruction of any samples taken and not tested, and the investigator must document this in the site study records.

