### 10.2.1. Populations for Analyses

For purposes of analysis, the following populations will be defined:

| Population            | Description   |
|-----------------------|---|
| Full population       | The Full Population will consist of all subjects who are enrolled in the study and attend Visit 1.                                    |
| Sub-cohort population | Subjects who are enrolled in the Biomarker & Digital sub-cohort and who provided a least one additional sub-cohort assessment.        |
| Completer Population  | The Completer Population will consist of all subjects in the Full Population who complete all scheduled clinic visits over 2.5 years. |

Other sub-populations may be defined based on disease severity, co-morbidities, age, gender, or subject phenotypes. This will be detailed in RAP.

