## 2. SUMMARY OF KEY PROTOCOL INFORMATION

### 2.1. Changes to the Protocol Defined Statistical Analysis Plan

There were changes to the original planned statistical analyses specified in the protocol amendment 02 (Dated:17JUN2021) of study 208630 [TMF-13816843].

The definition of population will follow the description of SAP, to better fit the study purpose. HRU population added due to data collection status.

Considering the COVID lockdown impact, analysis window for the 3 post-baseline visits (Month 6, Month 18, Month 30) will be changed to  $\pm 90$  days.

Rate of change (decline) in CAT score analysis will be performed in further post-hoc analysis.

Phenotype analyses will be descriptive only, and further analyses of phenotype may be performed post hoc and based on separate documents.

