### 17.5.2. Study Population

Demographics	
Age	
• Age will be calculated based on the Visit 1.	
• Birth date will be imputed as follows:	
• Any subject with a missing day will have this imputed as day '15'.	
• Any subject with a missing date and month will have this imputed as '30JUN'.	
• Birth date will be presented in listings as 'YYYY'.	
Age categories are based on at screening and are defined as:	
• <65 years	
• ≥65 years	

Subject disposition	
Discontinuation from Study Treatment	
Not Applicable.	

Subject disposition
Discontinuation from Study Treatment
Discontinuation from Study

Censoring will be performed as follows:
 
 
• For subject that withdraws consent for disclosure of future information, any data collected prior to withdrawal will be retained and reported.
 
• For subject that withdraws consent for disclosure, the site may use any publicly information to determine vital status at the end of the study and this information would be included in the final analyses.
 
• If a subject withdraws from the study, he/she may request destruction of any samples taken and not tested, such request will be documented in study records.
 
• Subject that is unreachable and fails to come back for both Visit 3 and Visit 4 will be considered lost to follow-up. Data collected prior to missed visits will be retained and reported.
 

Smoking status

 
• Smoking status: Never smokers are defined as those with a lifetime exposure of <1 package/year in their life (excluding passive smoker). Ever smokers (current or former) are defined as those with a lifetime exposure of <math>\geq 10</math> package/year. Former smokers are those who have stopped smoking for at least 6 months. Current smokers are those who are currently smoking. Passive smokers are defined as those with the presence of smokers living in the same household, or co-workers smoking nearby while indoors
 
• Smoking status will be reassessed at each scheduled clinic visit evaluated by participants' self-report (e.g. never smoker, current smoker, former smoker).
 
• Smoking history including Pack-years of smoking: Number of pack years (number of cigarettes per day / 20) x number of years smoked, e.g., 10 packyears means 20 cigarettes per day for 10 years, or 10 cigarettes per day for 20 years)
 

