**Microbiome****17.6. Appendix 6: Reporting Standards for Missing Data****17.6.1. Premature Withdrawals**

Element	Reporting Detail
General	
 
Subject study completion (i.e. as specified in the protocol) was defined as completed all scheduled visit and completed exit visit.
 
Withdrawn subjects were not replaced in the study.
 
All available data from participants who were withdrawn from the study will be listed and all available planned data will be included in summary tables and figures, unless otherwise specified.
 
Withdrawal visits will be slotted as per Appendix 3: Assessment Windows or will be summarised as withdrawal visits.
 

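### The SAP's Full Population excludes anyone who withdraws consent at any time, so data that the SAP's own appendix says will be reported have no place in the analyses

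*SAP*

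**What the plan says.** Protocol 10.2.1 defines the population by two conditions only: "The Full Population will consist of all subjects who are enrolled in the study and attend Visit 1". SAP Section 4, Table 2 adds a third and takes those "who are enrolled in the study and attend Visit 1, and not withdraw informed consent". It separately removes one participant who could not be assigned to any arm.

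On data already collected, protocol 8.2 states that, when consent for disclosure of future information is withdrawn, "the sponsor may retain and continue to use any data collected before such a withdrawal of consent". SAP 17.5.2 is firmer: "For subject that withdraws consent for disclosure of future information, any data collected prior to withdrawal will be retained and reported". Both sections add that, for someone who withdraws consent for disclosure, vital status found in public sources would enter the final analyses. SAP 17.6.1 says of withdrawn participants that "all available planned data will be included in summary tables and figures, unless otherwise specified".

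SAP 2.1 announces the change of populations in one line: "The definition of population will follow the description of SAP, to better fit the study purpose". It does not mention consent. The version-history entry for this amendment refers only to the template and the grouping of endpoints. The preceding RAP (amendment 2, included with the SAP) used the protocol's definition.

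**The concern.** Consent withdrawal can be known only after enrolment, so the clause makes membership depend on a later event. A participant who withdraws consent after the Month 18 visit would lose baseline, Month 6 and Month 18 data, although all were collected under valid consent.

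The reach is wide. Table 2 assigns the study population, disease progression, phenotypic, treatment and resource-use, and safety analyses to Full, and defines Sub-cohort and HRU as subsets of Full. If those who withdraw consent differ from those who stay, then baseline tables, exacerbation rates and FEV1 slopes describe a selected group. The exclusion also works against the plan's own missing-data strategy, which relies on keeping what was observed before a participant left.

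**Working it through.** **The rules side by side**

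| Place | Rule | Force |
|---|---|---|
| Protocol 10.2.1 | Enrolled and attended Visit 1 | Defines Full |
| SAP Section 4, Table 2 | As above, and consent not withdrawn | Defines Full; no time limit |
| Protocol 8.2 | Data before withdrawal of consent | May be used |
| SAP 17.5.2 | Data before withdrawal of consent | Will be retained and reported |
| SAP 17.6.1 | Available planned data of withdrawn participants | In tables and figures, with a proviso |
| SAP 15.1 | Deaths and procedure-related SAEs | Full Population only |

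**Death endpoint.** SAP 17.5.2 sends publicly sourced vital status of those withdrawing consent for disclosure into the final analyses. SAP 15.1 tabulates death in Full only. If such a person counts as having withdrawn informed consent, a death found this way has no table to enter. A procedure-related SAE before the withdrawal would likewise be missing from the listing.

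**Models.** The random coefficients model in SAP 8.1 assumes missing at random and needs one post-baseline value. A participant who withdraws consent after Month 6 spirometry could contribute to it, but is removed. SAP 17.6.2 plans multiple imputation for participants who withdraw, based on their own earlier measurements. For consent withdrawers the clause removes that input.

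**Planning figures (protocol 10.1.3)**

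- σ_p = √(3.8² + 12 × 3 × 233² / (2.5² × 4 × 5)) = 125.1, as stated.
- GOLD I vs GOLD II, half-width 15 mL/yr: N₁ = 1.96² × 125.1² × 2 / 15² ≈ 534.4, rounded up to 535. The plan states 525, which gives a half-width of 15.13.
- 525 / 0.75 = 700 enrolled per group, as stated.
- All COPD: 2 × 1.96 × 125.1 / √1275 = 13.7 mL/yr, as stated.

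These are calculated on completers. Someone who withdraws consent before Visit 4 is not a completer, so restoring such people to Full changes none of these figures.

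**Illustration only.** The documents give no consent-withdrawal rate, so the shares and slope differences below are assumptions. The shift in a group's mean slope is about share × difference in slope between withdrawers and the rest.

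| Share withdrawing consent | Removed of 2,000 | Shift if difference is 20 mL/yr | Shift if 40 mL/yr |
|---|---|---|---|
| 1% | 20 | 0.2 | 0.4 |
| 5% | 100 | 1.0 | 2.0 |
| 10% | 200 | 2.0 | 4.0 |
| 25% (ceiling) | 500 | 5.0 | 10.0 |

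The last row would require every planned dropout to be a consent withdrawal, and would extend the dropout allowance used in the COPD calculation to all 2,000. The shifts weight by persons. The model gives less weight to people with few visits, so its estimate would move less.

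**The case against.** The strongest defence is that Table 2 uses a term the SAP never defines. The documents distinguish withdrawal from the study, withdrawal of consent for disclosure of future information, withdrawal of consent for disclosure, and loss to follow-up. Withdrawing informed consent might mean a fifth case: full revocation, with refusal of any use of data already held. On that reading Table 2 and SAP 17.5.2 would not collide, and the exclusion would be proper. This is possible, but it is not in the text. Table 2 as worded covers any withdrawal of consent.

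The proviso in SAP 17.6.1 could also be read as making room for Table 2. SAP 17.5.2 has no such proviso. SAP 2.1 does announce that populations differ from the protocol, so the departure is disclosed, but the reason given does not reach consent.

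Four stronger readings are tempting and go beyond the documents.

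- A reader might infer that the protocol itself requires the data to be reported. Protocol 8.2 gives a permission; only SAP 17.5.2 gives an instruction.
- A reader might infer that all dropouts are deleted. Loss to follow-up and withdrawal for other reasons are not excluded by the clause.
- A reader might infer a bias of known direction. Nothing in the documents ties consent withdrawal to disease burden; mildly affected participants may leave because of visit burden.
- A reader might put a size on the exacerbation rate. Suppose 20–60% of the 25% dropout withdraw consent (5–15% of participants), at 1.5–2 times the rate of the others. Then 0.95 + 0.05 × 1.5 = 1.025 and 0.85 + 0.15 × 2 = 1.15, an understatement of 2.5–15%. Neither input has a source in the documents, and the formula gives withdrawers full follow-up, whereas SAP 7.1 uses a log time-on-study offset. With half the follow-up (also assumed), the ratios are (0.95 + 0.025 × 1.5) / 0.975 = 1.013 and (0.85 + 0.075 × 2) / 0.925 = 1.081, or 1.3–8.1%.

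It is also fair that anyone leaving before a post-baseline spirometry value is absent from the slope model under either definition, and that the study is mainly descriptive with no formal inference.

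**Conclusion.** The point stands on the wording alone. Taken literally, Table 2 removes participants on the basis of a post-enrolment event, departs from the protocol's definition without a stated reason for this clause, and leaves data that SAP 17.5.2 says will be reported with no population to be reported in. Every analysis except the All Screened summaries is affected, including deaths and procedure-related SAEs. The number affected and the size and direction of any bias cannot be derived from the documents, and the planned precision of 525 completers per group and 13.7 mL/yr is untouched. The conclusion assumes that the clause means what it says. If the sponsor intended only full revocation, the remaining defect is that the SAP does not say so. The change should be made, because the inconsistency is plain and the repair is small.

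**What to change.** Redefine Full in SAP Section 4, Table 2 as all enrolled participants who attend Visit 1 and can be assigned to an arm, with data used up to the date of consent withdrawal. The separate exclusion of the one unclassifiable participant remains.

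Exclude only participants who refused use of data already collected. Define that category and report its number by arm. Then align SAP 15.1 (deaths and SAEs), 17.5.2 (data before withdrawal and vital status), 17.6.1 (withdrawn participants in tables) and 17.6.2 (multiple imputation), and state the change and its reason in SAP 2.1.

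The cost is one sentence in Table 2, matching edits in those sections, and a rerun of the population flag and the outputs that depend on it. No new data and no change to the sample size are needed.
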